Based upon preliminary results from the ongoing Phase 1 clinical study AVXS-101-CL-101, at least 80% of treated symptomatic patients with bi-allelic *SMN1* deletions and 2 copies of *SMN2* without the *SMN2* gene modifier mutation (c.859G>C) are expected to achieve the co-primary efficacy endpoint of survival through 14 months of age. It is anticipated that 75% of patients in the PNCR [5] population would not survive beyond 13.6 months of age, and that these control patients will represent a 25% survival rate based upon the natural history of the disease. With this efficacy, an enrolled sample size of 15 patients that meet ITT criteria (assuming 30% of patients are excluded from the analysis) would provide power of >80% to detect a significant difference with $\alpha = 0.05$ using a two sample 2-sided Fisher's exact test, comparing to patient-level data drawn from a published natural history observational study dataset with patients who meet the eligibility criteria for this study (bi-allelic *SMN1* deletions, 2 copies of *SMN2*, age of onset ≤ 6 months of age). The natural history observational study dataset was collected by PNCR network from the study performed at three large, tertiary care centers in the United States (Harvard University, Columbia University, Children's Hospital of Philadelphia; PNCR).

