5.5. PNCR Control Population

The PNCR Natural History dataset ([Finkel, 2014](#)) is drawn from a large natural history study performed on a large cohort of 337 patients with any form of spinal muscular atrophy followed at 3 large, internationally recognized tertiary medical centers with significant expertise in the management of SMA (Harvard University/Boston Children's Hospital, Columbia University and the University of Pennsylvania/Children's Hospital of Philadelphia). Previously identified patients followed in PNCR site clinics and newly diagnosed patients were enrolled. All eligible patients were offered participation in the PNCR study. Study visits were scheduled at baseline and at 2, 4, 6, 9, and 12 months and every 6 months thereafter. The SMA standard of care guidelines published in 2007 were used as a basis for providing uniform care among the study sites. For purposes of this study, sitting (for SMA Type 2) was defined as being able to sit independently for >10 seconds;

children who were unable at any point to achieve this milestone were classified as SMA Type 1.

A natural history control population is drawn from the PNCR Natural History Dataset ([Finkel, 2014](#)) consisting of all patients with age of onset \leq 6 months, bi-allelic deletion of *SMN1* (exon 7/8 common homozygous deletion) and 2 copies of *SMN2* for whom enrollment data (retrospective and prospective) is available to determine survival based on the defined criteria. The *SMN2* modifier mutation (c.859G>C) described by Prior and colleagues (Prior, Thomas W., et. al. "A positive modifier of spinal muscular atrophy in the *SMN2* gene." *The American Journal of Human Genetics* 85.3 (2009): 408-413.) was not assessed in the PNCR study cohort. Based on these criteria, 23 patients from the PNCR dataset are included in the control population. Among them, 17 patients reached the combined endpoint of death or the need for a minimum of 16 hours/day of noninvasive ventilation support for a minimum of 14 continuous days by 13.6 month of age. The survival rate at 13.6 months of age is approximately 25% (17/23), of which the control cohort will be used as comparator with ITT population for survival analysis.

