6.2.4. Derived and Transformed Data

6.2.4.1. Primary Efficacy Variables

The co-primary efficacy endpoint is functional independent sitting at the 18 months of age visit.

Functional independent sitting: this is assessed by video evaluation by an expert reviewer of videos taken either at scheduled visits (see

Table 4 and

Table 5) or provided by parent/legal guardian, if patient meets the criterion:

- Child sits alone without support for at least 30 seconds. This will be collected from external dataset.

The other co-primary endpoint, event-free survival, is defined as avoidance of any one of the following events up to 14 months of age, whichever occurred first:

- Death, *or*
- Tracheostomy, *or*
- Noninvasive Ventilatory support \geq 16-hour per day *and* continuously \geq 14 days

Usage data for patients using non-invasive ventilatory support will be extracted directly from the device (Triology 100, Trilogy 200) on an SD card, and transferred as an external dataset. Average daily use of non-invasive ventilatory support by visits (if available) will be calculated. If a patient did not have a Trilogy device at baseline and was using non-invasive ventilatory support prior to screening, the average daily usage will be based on parent report and documented in the source documentation. As a secondary analysis, the amount of ventilation support will be categorized into None, >0 - \leq 12 hours, >12 - $<$ 16 hours, \geq 16 or permanent ventilation. The count and percent of patients in each ventilation support category at each visit (if available) will be displayed.

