The co-primary efficacy endpoint is defined by avoidance of the combined endpoint of either (a) death or (b) permanent ventilation, defined as requirement of tracheostomy or ≥ 16 hours of respiratory assistance per day (includes non-invasive ventilatory support) continuously for ≥ 14 days in the absence of an acute reversible illness, excluding perioperative ventilation. Permanent ventilation, so defined, is considered a surrogate for death.

Non-invasive ventilatory support usage data will be extracted directly from each patient's device; the data will be downloaded from the device's SD card through software provided by the

manufacturer and transferred as an external dataset. Each patient will also be assessed by investigator whether permanent ventilation criteria has been met, which is the primary endpoint. If the permanent ventilation criteria are met, the event (surrogate for death) will be reported in [REDACTED] system for primary efficacy analysis.

An “acute reversible illness” is defined as any condition other than spinal muscular atrophy that results in increased medical intervention (i.e., increased requirement for external ventilator support; use of other concomitant meds as rescue) requirements and is expected to be reversible or improved following definitive intervention (i.e., surgery, antibiotics) or introduction of escalated supportive care, such as hospitalization (i.e., for upper respiratory infection, spontaneous fracture). The specific duration of the condition antecedent intervention shall not be considered in the definition of “acute”. The date of “definitive intervention” shall be defined as the date of provision of a procedure (i.e., surgery, etc.) or medication (i.e., antibiotics) intended to cure or substantially improve the condition. For conditions, such as viral respiratory infections, for which supportive care is provided, the date of “definitive intervention” shall be considered the date of hospitalization or substantial escalation of care.

“Perioperative” use reflects any alteration of ventilator use related to a surgical or other medical procedure of any nature for which the participant received medications that could impair or interfere with respiratory function.

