For a participant who develops an acute reversible illness and/or requires perioperative ventilator support, a recovery period not to exceed 21 days following the date of definitive intervention will be instituted. Following this recovery period, the condition will be considered sub-acute and the participant will become evaluable with regards to the surrogate survival endpoint (Requirement of ventilator support of ≥ 16 hours/day for greater than 14 days).

Example: Using this approach it would mean that on day 1, patient A receives definitive intervention for an acute reversible illness resulting in ventilator support for ≥ 16 hours/day. Days 1-21 will be provided to permit recovery from the acute reversible illness. On Day 22, the participant is no longer considered to have an acute illness. Should the participant continue to require ≥ 16 hours/day of ventilator support from day 22 to day 36, he or she shall be considered to meet the surrogate endpoint.

Statistical approach: The proportion surviving event-free to 14 months of age will be computed in the ITT population. Patients who terminate the study prior to reaching 14 months of age for any reason will be considered treatment failures (event).

As a comparator, in a natural history study of SMA Type 1 patients, [Finkel et al \(2014\)](#) estimated that only 25% of SMA Type 1 patients with 2 copies of *SMN2* would survive event-free to 13.6 months of age.

The observed proportion surviving in the current study will be compared to the natural history data [\(5\)](#) of the matching cohort using a two-sample Fisher’s exact test, along with the corresponding 95% confidence intervals.

If status at 14 months of age is coded using variable SURVIVE as 1 if patient survived to 14 months of age without requiring permanent ventilation, and 2 otherwise, then the SAS code to generate the endpoint analysis is:

```
proc format;  
value survive  
1= 'Yes'  
2= 'No'  
;  
Value grp  
1='AVXS'  
2='PNCR'  
;  
run;  
proc freq data=x order=data;  
table grp*survive / measures riskdiff;  
exact fisher / alpha=0.05;  
run;
```

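### The SAP defines the permanent-ventilation event of the survival co-primary inconsistently and does not show that the same rule was applied to the PNCR controls

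*SAP*

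**What the plan says.** **Treated patients.** Section 8.1.2 counts death, tracheostomy, or at least 16 hours of respiratory assistance a day for at least 14 days, "in the absence of an acute reversible illness, excluding perioperative ventilation". Sections 3.1 and 4.1.1 agree. The glossary in Section 1.2 has the exclusions but does not name tracheostomy. Section 8.1.2 adds that after an acute reversible illness or procedure "a recovery period not to exceed 21 days following the date of definitive intervention will be instituted", after which the child becomes evaluable again.

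**Day count.** Section 8.1.2 first requires at least 14 days. When it describes the end of the recovery period it requires more than 14. Its example concerns a child who still needs "ventilator support from day 22 to day 36, he or she shall be considered to meet the surrogate endpoint".

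**Derived variable.** Section 6.2.4.1 says that event-free survival "is defined as avoidance of any one of the following events up to 14 months of age, whichever occurred first". It then lists death, tracheostomy, and non-invasive support of at least 16 hours a day for at least 14 days. No illness exclusion, perioperative exclusion or recovery period appears.

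**Controls.** Section 5.5 reports that 17 of 23 PNCR patients either died or had a "need for a minimum of 16 hours/day of noninvasive ventilation support for a minimum of 14 continuous days by 13.6 month of age". It mentions no exclusions, recovery period or tracheostomy. It does say that controls were chosen because their data allow survival to be judged by the criteria as defined.

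**The concern.** The survival co-primary is a Fisher test of treated patients against an external control group, so it is interpretable only if an event means the same thing in both groups. Two problems arise.

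First, the treated event itself can be scored in more than one way. A child on at least 16 hours a day for days 1 to 14 of a respiratory infection is an event under Section 6.2.4.1 and not under Section 8.1.2.

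Second, the only description of the control count matches the stricter scoring of ventilation. If that description is complete, the same course would count against a control and not against a treated child.

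The treated event is also open to judgement. By Section 8.1.2 it rests on the investigator's assessment in an open-label study, whereas Section 4.1.1 requires independent confirmation for the sitting milestone. The survival test also gates both secondary endpoints (Section 8.4).

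**Working it through.** **1. Definitions side by side**

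| Element | Section 8.1.2 (treated) | Section 6.2.4.1 (derived variable) | Section 5.5 (control count) |
|---|---|---|---|
| Hours per day | ≥16 | ≥16 | ≥16 |
| Duration | ≥14 days, then >14 days, then days 22–36 | ≥14 days | ≥14 days |
| Illness and perioperative exclusion | yes | not stated | not stated |
| Recovery period | up to 21 days | not stated | not stated |
| Tracheostomy | event | event | not stated |
| Cut-off | 14 months | 14 months | 13.6 months |

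**2. Day count.** Days 22 to 36 inclusive are 36 − 22 + 1 = 15 days; fourteen days from day 22 end on day 35. Take an illness episode with support from the day of intervention and the full 21-day recovery. The event falls on day 35 (≥14 days) or day 36 (the example), against day 14 under the plain rule. The delay is 35 − 14 = 21 or 36 − 14 = 22 days, and a child who comes off support in between is never counted.

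**3. The SAP's own power figure.** Inputs from Section 3.7: event-free survival in "at least 80% of treated symptomatic patients"; for the comparator, "these control patients will represent a 25% survival rate"; 15 ITT patients with 30% excluded, so 15 × 0.70 = 10.5, taken as 10 or 11; two-sided Fisher test at 0.05; stated power above 80%. From Section 5.5: 23 controls with 17 events, so 6/23 = 26.1% event-free. (Section 5.5 prints 17/23 beside the approximate 25%, but 17/23 = 73.9% is the event fraction.)

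Power = Σx Σy Bin(x; n, 0.80) · Bin(y; 23, pC) · 1[Fisher p(x, y) ≤ 0.05]

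| n treated | pC = 25% | pC = 6/23 |
|---|---|---|
| 15 | 92.9% | 91.7% |
| 11 | 84.6% | 82.7% |
| 10 | 82.4% | 80.2% |

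The stated figure reproduces. The point concerns the event definition, not the power claim.

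**4. If a common rule added treated events.** Controls held at 6/23. The starting values are the SAP's assumed 80%: 0.80 × 15 = 12 and 0.80 × 10 = 8.

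- n=15: 12/15 p=0.0023; 11/15 p=0.0073; 10/15 p=0.020; 9/15 p=0.049; 8/15 p=0.168.
- n=10: 8/10 p=0.007; 7/10 p=0.026; 6/10 p=0.114.

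From 12/15, three reclassified children leave significance intact and a fourth removes it. From 8/10, the second removes it.

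**5. If a common rule removed control events.** The SAP does not say how many of the 17 events were ventilation events or arose in an acute or perioperative episode. The number removed, k, is therefore an assumption, shown as a range with (6 + k)/23 controls event-free.

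| k | p at 12/15 | Power, n=15 | Power, n=11 | Power, n=10 |
|---|---|---|---|---|
| 0 | 0.0023 | 91.7% | 82.7% | 80.2% |
| 1 | 0.0069 | 85.5% | 74.0% | 70.6% |
| 2 | 0.0089 | 77.4% | 63.8% | 60.2% |
| 3 | 0.020 | 67.7% | 52.9% | 49.8% |
| 4 | 0.043 | 56.9% | 41.9% | 39.9% |
| 5 | 0.088 | 45.8% | 31.7% | 30.8% |

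**6. False positives.** Suppose there is no true difference (both 26.1%, 15 against 23) and scoring alone adds 0, 5, 10, 15 or 20 points to treated survival. The test then rejects in 2.9%, 4.6%, 8.2%, 13.8% or 21.8% of trials. These shifts are assumed; nothing in the SAP fixes their size.

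**The case against.** A reader might infer that the controls were scored by a plain 14-day rule and that the endpoint therefore differs by arm in the product's favour. The SAP does not support that as fact.

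- Section 5.5 is a one-sentence summary of a result, and its selection wording suggests that a common definition may have been intended. The code in Section 8.1.2 uses one survival variable for both groups, described in terms of permanent ventilation, which is defined elsewhere with the exclusions. Unequal scoring is undocumented, not shown.
- Section 6.2.4.1 conflicts with Section 8.1.2 within the treated group. If it governed, the ventilation rule would match Section 5.5. Section 4.1 also points to Section 8 for details.
- The recovery period is also a cap: it limits how long an illness can keep a child from being evaluable.
- It is tempting to say that a treated child ventilated for 35 straight days after an infection is event-free. Under the ≥14-day rule, days 22 to 35 make that child an event; the statement holds only on the >14-day wording.
- Several differences work against the product. Tracheostomy is a named event only for treated patients, and early termination for any reason counts as an event. Follow-up runs to 14 rather than 13.6 months, which is 0.4 × 30 = 12 days longer by the SAP's 30-day month.
- At the assumed 80% survival the result tolerates several reclassifications.

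All of this stands, and it limits the claim. It does not supply the missing statement. The SAP nowhere says that the exclusions and recovery period were, or could be, applied to PNCR records, which are partly retrospective. The sensitivity analyses in Sections 6.3 and 8.1.2 address missing data, dropout and time to event. Section 4.8 only permits further natural-history comparisons.

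**Conclusion.** The concern holds in a limited form. The permanent-ventilation event is defined inconsistently across Sections 1.2, 6.2.4.1 and 8.1.2, the day count conflicts within Section 8.1.2, and the rule used for the 23 controls is not documented.

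If the controls were scored by the plain rule of Section 5.5, the ventilation component favours the product. With the other differences running the opposite way, neither the net direction nor the size of the bias can be established from the SAP.

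As a scale only: at the assumed 80% treated survival, it takes four reclassified treated children of 15, or two of 10, to lose significance against 6/23. On the control side, 12/15 loses it at five reclassified events, but power drops below 80% after two (n=15) or one (n=10 or 11). These counts are assumptions, not estimates. The point should be fixed; confidence is medium.

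**What to change.** 1. Reconcile Sections 1.2, 5.5, 6.2.4.1 and 8.1.2 into one endpoint-scoring rule with one day count, and make the worked example agree with it.
2. State whether the illness and perioperative exclusions, the recovery period and tracheostomy were applied to the 23 PNCR patients, and apply them where the records allow.
3. Pre-specify a sensitivity Fisher test that scores both groups by one common rule, and report it beside the primary result. If the PNCR records support nothing more, use the plain rule of Section 5.5 for both.

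The wording changes and the extra test are cheap. The real cost is re-scoring some treated ventilation episodes. Section 4.6.10 provides for daily hours when the permanent-ventilation criteria are met, and otherwise from device cards where that device is used, so gaps are possible and should be listed. The treated event-free rate may come out lower.

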8.2. Secondary Efficacy Endpoint(s) and Analyses

8.2.1. Co-secondary Efficacy endpoint: Maintain ability to thrive

At baseline, a patient will be defined as not requiring parenteral nutrition if the child, 1) does not use parenteral nutrition of any kind (i.e., gastrostomy, nasogastric tube, nasojejunal tube, etc.); and 2) demonstrates intact swallowing on baseline assessment such that the child does not receive a recommendation for implementation of parenteral nutrition prior to receipt of AVXS-101.

The proportion of patients who at baseline do not require parenteral nutrition (as defined) who maintain the ability to thrive at the time of the child's study visit when he or she reaches 18 months of age will be summarized by subgroup and overall in the ITT population.

The ability to thrive is defined by meeting all of the following criteria:

- the ability to tolerate thin liquids as demonstrated through a formal swallowing test
- does not receive nutrition through mechanical support (i.e., feeding tube)
- maintains weight (>third percentile for age and gender as defined by WHO guidelines) at 18 months of age.

A patient who is not required mechanical support to receive nutrition at the date of 18 months of age visit is considered to meet the feeding criterion.

A one-sided Exact Binomial Test will be used to test the null hypothesis of $p=0.1\%$ at significance level of 0.025. Furthermore, the corresponding one-sided 97.5% confidence interval will be estimated by the exact method.

In case for the presence of missing value, sensitivity analyses outlined in [Section 6.3](#) will be carried out to evaluate the appropriateness of the assumption for missing data.

Additionally, the proportion of patients meeting each of the criteria will be summarized.

A large grid of black bars on a white background, likely a placeholder or redacted content. The grid consists of approximately 20 horizontal rows and 20 vertical columns, creating a dense pattern of black rectangles. There are a few small breaks in the pattern, such as a single bar missing in the second row and a small cluster of bars missing in the fourth row.

8.4. Multiplicity

The primary and secondary efficacy hypotheses are to be tested in a hierarchy approach that specifies the order in which they are to be evaluated. This strategy requires that only when first co-primary endpoint meets significance will the second co-primary endpoint be tested;

only when the first co-secondary endpoint meets significance will the second co-secondary endpoint be tested; only if both primary endpoints meet significance will the secondary endpoint be tested. The order of testing will be: first, functional independent sitting (first co-primary endpoint); second, event-free survival (second co-primary endpoint); third, maintenance of ability to thrive (first co-secondary endpoint); fourth, independence from ventilator support (second co-secondary endpoint). Such pre-specification of the order of testing within hierarchical framework strongly prevents type 1 error inflation due to multiplicity.

9. ANALYSIS OF PHARMACOKINETICS

Not applicable to this SAP.

10. SAFETY

10.1. Extent of Exposure

The actual, weight-adjusted dose, in vg/kg, of AVXS-101 administered during the infusion will be summarized, as well as the site of infusion, duration of infusion, whether the entire volume was delivered, and whether the infusion was interrupted.

10.2. Treatment Compliance

Weight-adjusted dose of AVXS-101 administered and dosing compliance will be summarized.

The treatment compliance of each patient at Baseline will be calculated as:

Percentage of compliance (%) = 100% * total volume administered / planned dose

The treatment compliance will be summarized by actual product received.

10.3. Adverse Events / Adverse Drug Reactions

10.3.1. Treatment-Emergent Adverse Events

Adverse events will be coded using the Medical Dictionary for Regulatory Activities (MedDRA). Treatment-emergent adverse events are defined as any event that begins or worsens in severity after initiation of study drug through the last study visit. If an incomplete onset date was collected for an adverse event, the event will be assumed to be treatment-emergent, unless there is other evidence that confirms that the event was not treatment-emergent (e.g., the event end date was prior to the study drug start date).

10.3.2. Tabulations of Treatment-Emergent Adverse Events

Adverse event data will be summarized and presented using primary MedDRA system organ classes (SOCs) and preferred terms (PTs) according to the version of the MedDRA coding dictionary used for the study at the time of database lock. The actual version of the MedDRA coding dictionary used will be noted in the clinical study report. The system organ classes will be presented in alphabetical order and the preferred terms will be presented in alphabetical order within each system organ class.

Adverse events will be presented using Safety Set.

